13.4.2 Data sources

The primary sources of data for this analysis will be from the point-of-care HbA1c testing done on site at the food pantries and the participant survey data, both at baseline and follow-up. In our assumptions, rolling enrollment lasted for approximately 6 months, and the length of follow-up between baseline and follow-up was also approximately 6 months (4-9 months overall).

13.4.3 Hypotheses

We are testing several hypotheses in this study.

1. The primary hypotheses which we are powered to examine is a significant improvement in HbA1c over a 6-month timeframe.
 - a. For all of these outcomes, we also hypothesize that the effect sizes will be largest among those who completed a minimum amount of exposure to all intervention components. A priori, we defined engagement in the intervention components as: picking up 80% of diabetes-appropriate food boxes, attending the 2 required diabetes education classes, and having at least 1 primary care visit over the 6-month follow-up period.
 - b. We also hypothesized that the intervention would have the largest effect on those in the poorest A1c control (>9%) and those with very low food security status at baseline.
2. Secondary hypotheses: The secondary outcomes of interest are improvements in fruit/vegetable intake, diabetes distress, self-reports of severe hypoglycemic events, depressive symptoms, medication adherence, tradeoffs between affording food vs medication/supplies, food security status, and food stability.
3. Healthcare utilization hypotheses/analyses will be covered in a separate analysis plan

13.4.4 Statistical analyses

For all the outcomes specified above, we will determine significant improvements using an ANCOVA specification:

$$Y_{i,t=1} = \beta_0 + \beta_1 T_i + \pi Y_{i,t=0} + \varepsilon_i$$

Where $Y_{i,t=1}$ is the given outcome variable measured post-treatment, $Y_{i,t=0}$ is its baseline value, T_i is an indicator for being assigned to treatment, and ε is the error term. Since randomization is at the individual-level, HuberWhite standard errors will be used. β_1 will provide the intent-to-treat effect.

Loss to follow-up

We intend to collect follow-up data on at least 80% of participants. We will conduct a formal missingness investigation to determine if the attrition rate differed between intervention and waitlist groups. If treatment status is found not to significantly affect attrition at the 5 percent significance level, then all estimation will proceed without any adjustment for attrition. If attrition is found to be related to treatment status, we postulate that attrition will be higher for the control group, and will employ Lee bounds to obtain bounds on our treatment estimates which are robust to this attrition (<https://ideas.repec.org/c/boc/bocode/s457477.html>). Multiple imputation for missing outcome data will also be explored as sensitivity analyses (<http://aje.oxfordjournals.org/content/175/3/210.full>).

Per protocol/exposure to treatment

Among those with complete baseline and follow-up A1c ascertainment, we will also examine the influence of the amount of exposure to the program. Specifically, we will determine whether the

participants who met our criteria for being “engaged” in the program (overall and by specific intervention component) had larger effects than those who were less engaged.

In this analysis, because the randomization benefits will be lost, we will adjust for other covariates in our model that we hypothesize to influence A1c and self-management improvements: age, gender, race/ethnicity, educational attainment, language, and site/location.

Subgroup analyses

While we are randomizing within sites, we also plan to conduct subgroup sensitivity analyses by both adjusting for site and examining changes within site to determine differential effectiveness by location. Site-specific differences will be shared with the food banks, but only reported publicly in manuscripts if found to be significantly different.

Other planned subgroup analyses (as specified in our hypotheses) are by baseline glycemic control (>9%) and food security status.

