3.4.1 DSME Group Classes

For the purposes of this study our assumptions are that a majority of study participants will be linked to a primary medical home to receive ongoing diabetes clinical care and chronic disease management, and a majority of study participants will (or should) be receiving basic DSME from existing clinic services at their primary medical home. However, based on our experience in the diabetes pilot project, we know that many participants may not receive DSME as part of their primary care, or clinic-based DSME messages may not be appropriate or relevant for this population.

Rationale behind FAITH-DM DSME Group Classes: Based on prior experience attempting to conduct group DSME classes with food pantry clients, we have learned that it is difficult to run formal class series that meet more than 3-4 times. We have thus decided to tailor our DSME program to focus on elements of diabetes self-management that are particularly important and specific to low-income populations facing food insecurity, with the understanding that existing health care clinic services will address traditional DSME messages and support. While we plan on addressing information on all AADE7™ Self-Care Behaviors, we will conduct a 2-class series emphasizing: healthy eating, problem solving, healthy coping, and risk reduction (prevention of diabetes-related complications), with a third open monthly forum session for further group discussion, support for the challenges of living with diabetes, reinforcement of problem-solving skills, and troubleshooting by participants.

Key Metrics for DSME Program Selection and Adaptation

1. Relevance for participant population
2. Flexibility to be tailored to heterogeneity of participant group
3. Cost
4. Translation into Spanish
5. Materials for participant distribution and training of facilitators

Intervention participants will be asked to sign up for a group DSME Class series at the time of their enrollment into the study. Prior to a participant's first class session, food bank staff will send out reminder postcards and make reminder phone calls. Template postcards will be provided and a script for reminder phone calls will be given to staff and volunteers making those calls. (See **Appendix AD** for a sample of the post card with text.)

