To help maximize attendance at Sessions 1 and 2, sites will offer supplies to participants in attendance to support their diabetes self-management. Supplies will include items such as water bottles, measuring cups, re-usable grocery bags, cookbooks, medication pill boxes, foot mirrors, pedometers, and stress balls. Grant awards include funding for these items.

Group classes (including the monthly drop-in sessions) are only offered to participants randomized to the intervention group.

Group Classes

Group classes will be offered twice each month (or as needed) at varied days, times, and locations to maximize attendance. Classes will be conducted in English and Spanish by trained health educators. Each class session lasts 2 – 2.5 hours, and a class series will include 2 sessions with follow-up drop-in sessions for ongoing support. Class structure will emphasize participant involvement, group discussion and interaction, participant teachback, use of visual aids, and repetition of clear, simple messaging around key self-management strategies.

Class sessions will be scheduled so that all study participants can complete session 1 within 1 month of their enrollment date, and session 2 within 2 months of their enrollment date.

Session 1: Introduction to Diabetes – provide participants with basic information needed for diabetes self-management including disease overview, healthy eating strategies, physical activity, blood sugar monitoring, and treatment plans. Primary AADE7™ behaviors addressed: Healthy Eating, Physical Activity, and Monitoring.

Session 2: This session will focus on living with diabetes given the challenges of food insecurity and other common issues for food pantry clients. Primary AADE7™ behaviors addressed: Problem Solving, Healthy Coping, and Risk Reduction.

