Drop-in Open Forum Sessions: These sessions will be offered once monthly (in both English and Spanish and in as many geographic areas as needed) and facilitated by food bank nutrition education staff. The goal of the drop-in classes is to create a space for participants to receive ongoing support, practice problem-solving skills, develop health care connections, etc. The forum sessions are also opportunities for sites to respond directly to participant needs and interests. A secondary objective in offering open forum sessions is to help foster a participant support structure whereby food pantry participants can benefit from one another's experiences, skills, and strategies on diabetes self-management. Each session should last 60-90 minutes.

Drop-in sessions are for study participants in the intervention arm, and participants should be encouraged to attend all sessions while they remain in the study. Monthly reminder calls and flyers during food distributions are useful strategies for increasing attendance. Additionally, food bank staff should encourage study participants to attend the sessions with a family member or a support person.

These monthly sessions can focus on a variety of topics related to diabetes self-management education and support. Food bank staff can draw from existing nutrition education programming and adapt materials to target study participants. Example session topics include:

- Healthy eating and MyPlate
- Healthy eating: rethink your drink
- Healthy eating: grocery store tour
- Healthy eating: label reading and carbohydrate counting
- Healthy eating on a budget
- Physical activity: walking program

- Goal setting and action plans

Additionally, sites are encouraged to build on existing connections with local community health care providers to involve clinicians as guest speakers during monthly sessions. Clinicians and practitioners can be invited to participate in 1-2 sessions during a 12-month period. Examples of topics and providers include:

- Stress management (social worker, therapist)
- Depression and healthy coping (social worker, therapist)
- Diabetes and eye health (ophthalmologists)
- Diabetes and dental health (dentist)
- Diabetes and foot health (podiatrist)
- Diabetes medications overview (RN/CDE, MD)
- Physical activity alternatives (yoga instructor, zumba instructor, dance instructor)
- Smoking cessation (local provider)

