12.3.6 MS Access database instructions

This study uses Microsoft Access databases to store tracking information. Specifically, the Microsoft Access database will have the following forms and sub-forms:

- Screening form (for all individuals screened): Screening will be completed on paper forms; study staff is responsible for entering data on each individual screened from paper forms into Access databases at the end of each day.
- Baseline data and participant status form (for all individuals enrolled): This form is completed after initial enrollment of a study participant and is the only form in which study staff can edit participant status.
- Contacts Form: This form will contain all contact information for the participant
- PCP Contact Form: This form will contain all the contact information for a participant's PCP
- Study Data Forms
 - HbA1c form: Record all HbA1c values here
 - Food boxes form: Record all data on participant food box pick-up here
 - Education sessions form: Record all data on participant class attendance here
 - Primary care contact form: Record all data on contact study staff has with primary care here
- Study Data – Browse Only: When study staff need to retrieve, but not edit, data, use this form
- Reports: Study staff use this form to run reports on collected data
- Utilities: This option is used to make changes to the database, such as adding a new interviewer
- Close database: This form safely closes the database

Microsoft Access tracking forms can be used offline and uploaded to the FAITH-DM folder using VPN at the end of each day. It is important that all data is entered each day and securely saved and uploaded to the FATIH-DM folder using the instructions outlines in section 13.1.1.

13 Data Management

It is the food banks' responsibility to ensure that all forms are complete, intact, and transmitted to the Coordinating Center, as appropriate:

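### Shared classes in the intervention arm alone can correlate outcomes after randomization; the primary standard error makes no allowance for this, and individual randomization is not a reason to omit it

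*Combined protocol and SAP*

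**What the plan says.** The primary model in section 13.4.4 regresses follow-up HbA1c on treatment and baseline HbA1c. On the standard error it says "Since randomization is at the individual-level, HuberWhite standard errors will be used". Section 13.5.4 gives the same reason for the utilization analysis. Neither section has a class or educator term or a cluster-robust variance, and the sample size in 13.4.1 contains no ICC. Adjustment for site appears only as a sensitivity analysis.

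Section 3.4.1 describes a component delivered in groups to one arm:

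- Who gets it: "Group classes (including the monthly drop-in sessions) are only offered to participants randomized to the intervention group". Controls do not get it after their waiting period either.
- How groups form: "Intervention participants will be asked to sign up for a group DSME Class series at the time of their enrollment into the study".
- Structure: "a class series will include 2 sessions with follow-up drop-in sessions for ongoing support".
- Frequency and place: "Group classes will be offered twice each month (or as needed) at varied days, times, and locations to maximize attendance".
- Delivery: "Classes will be conducted in English and Spanish by trained health educators".
- Intended interaction: one aim of the drop-in sessions is to "help foster a participant support structure".

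Attendance is captured. Section 12.3.6 lists among the Access forms "Education sessions form: Record all data on participant class attendance here".

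**The concern.** Individual randomization makes assignments independent. It does not keep outcomes independent once a treatment is delivered in groups. If some classes go better than others, because of the educator or the mix of participants, classmates' HbA1c values move together, and only in the intervention arm. Huber-White errors correct for unequal residual variances but set the covariance between participants to zero.

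If the class-induced correlation is positive, the reported interval for the primary effect is too narrow and a test at nominal 5% rejects too often. The sample size of 300 per arm rests on the same independence assumption, so power is overstated as well.

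**Working it through.** **Step 1: reproduce the plan's figure.** Inputs from section 13.4.1: difference 0.4; SD 1.6 (mean 9.5) and 1.9 (mean 9.1, the treated arm); correlation 0.51; two-sided alpha 0.05; power 90%.

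- SD adjustment: √(1 − 0.51²) = 0.860, giving adjusted SDs of 1.376 and 1.634.
- Adjusted variances: 1.894 and 2.671, sum 4.565.
- n per arm = (1.960 + 1.282)² × 4.565 / 0.4² = 10.507 × 4.565 / 0.16 = 299.8, rounded up to 300. This agrees with the plan, so its calculation leaves no room for clustering.
- Planned SE = √(4.565 / 300) = 0.123; 95% half-width 0.242.

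**Step 2: a range for class size (assumed).** The target of 240 per site gives about 120 intervention participants per site. The timeline in 2.7 has 11 enrollment months (October 2015 to August 2016), so 120 / 11 ≈ 11 per month. One series a month gives m = 11. Splitting by language, or running two series a month, gives about 5. The 11 counts people enrolled. With 300 analysed per arm there are 100 per site and 100 / 11 ≈ 9 per series, so 11 is the upper end.

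**Step 3: the ICC (assumed).** The range is 0.01 to 0.05, read as correlation caused by the shared class.

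**Step 4: one-arm inflation.** With DE = 1 + (m − 1) × ICC applied to the intervention arm only:

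- SE ratio R = √[(1.894 + 2.671 × DE) / 4.565]
- Type I error = 2 × [1 − Φ(1.96 / R)]
- Power = Φ(0.4 / (0.1234 × R) − 1.96)

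| m | ICC | DE | R | Type I error | Power at 300 per arm |
|---|---|---|---|---|---|
| 5 | 0.01 | 1.04 | 1.01 | 5.3% | 89% |
| 5 | 0.02 | 1.08 | 1.02 | 5.5% | 89% |
| 5 | 0.05 | 1.20 | 1.06 | 6.4% | 87% |
| 8 | 0.05 | 1.35 | 1.10 | 7.4% | 84% |
| 9 | 0.05 | 1.40 | 1.11 | 7.8% | 83% |
| 11 | 0.05 | 1.50 | 1.14 | 8.5% | 81% |

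For the last row, (1.894 + 2.671 × 1.5) / 4.565 = 1.293 and √1.293 = 1.137.

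**Step 5: partial attendance.** If half the arm attends and the rest are unclustered, DE = 1 + 0.5 × (m − 1) × ICC. With m = 8 and ICC 0.05, R falls to 1.05 and the type I error to 6.2%.

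**Step 6: simulation.** ANCOVA with Huber-White errors, 4000 replicates per setting. The mean reported SE stays at 0.123 throughout. The true SD of the estimate is 0.129 at m = 5 and 0.136 at m = 8 (ICC 0.05 in both). Type I error is 5.05% with no clustering, 5.9% at m = 5 and 6.7% at m = 8.

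**The case against.** The strongest objection is that classes are sorted by language, place and time, so classmates would be alike even if the class did nothing. A reader might infer that any resemblance among classmates makes the interval too narrow. That does not follow. Likeness that predates randomization is shared across arms, and randomization in blocks within site protects the comparison. Only what the class itself adds counts. This part of the objection stands.

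It also bears on the remedy. Clustering the intervention arm by series, with controls as singletons and no site or language term, charges the pre-existing likeness to one arm. In simulation with a pre-existing ICC of 0.05 and no class effect, that approach gave a type I error of about 3.4%, which is too conservative. Adding site and language as covariates brought it back to about 5.5%. The objection therefore changes the remedy but does not remove the need for one.

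Other limits stand:

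- The excess type I error refers to a zero average effect with class effects varying around it. If the program changes nobody's HbA1c, classes create no correlation.
- The documents do not say that a series is a closed group with one educator. Section 14.3 lets qualified volunteers lead session 1, session 2 or both.
- Much of the peer support happens in drop-in sessions, which mix people from different series.
- Classes belong to one of four intervention components, and attendance will be incomplete.
- Sign-up is requested at enrollment, but the Access description mentions attendance and no sign-up field.

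**Conclusion.** The concern holds in conditional form. The reason given for the variance estimator is insufficient: allocation by individual does not make outcomes independent in an arm treated in groups. Neither the analysis nor the sample size allows for correlation created by the classes.

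The size is not known. Under the assumed ranges (5 to 11 per series, ICC 0.01 to 0.05, full attendance, the plan's SDs), the true SE is 1 to 14% above plan, the type I error 5.3 to 8.5%, and power 89 to 81%. The low end is negligible. The top end needs one series a month with no language split and everyone attending.

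A reader might go further and conclude that the primary test is shown to be invalid or the trial underpowered. The documents do not support that, because they give no class size and no ICC. What they support is prespecifying an analysis that remains valid whichever part of the range applies. This should be changed, with medium confidence in its practical importance.

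**What to change.** In section 13.4.4:

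1. Add site (the randomization stratum) and language as covariates in the primary ANCOVA.
2. Replace the Huber-White standard error with a small-sample cluster-robust one. For each intervention participant the cluster is the class series signed up for at enrollment, whether or not the person attends, which keeps the analysis by assigned arm. Each control, and any intervention participant with no series, is a cluster of one.
3. Report the estimated ICC.
4. Apply the same rule to the survey-based secondary outcomes.

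In the Access database, keep the ID of the sign-up series beside the attendance record.

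A partially nested mixed model, with a random intercept for series in the intervention arm only, is a close alternative but not an equivalent one. It reweights observations and can move the estimate, whereas the cluster-robust variance leaves the ANCOVA estimate as it is.

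The cost is SAP wording and one retained field. Intervals will be slightly wider, and clusters defined by series will not capture mixing across series in the drop-in sessions.

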13.4 Data Analysis Plan

13.4.1 Sample size estimation

We used the sampsi program in Stata to calculate the necessary sample size to detect a 0.4% decrease in HbA1c with 90% power. Using our preliminary data from the pilot phase of this project, we projected that the average A1c would decrease from 9.5% to 9.1% with a correlation between the

2 observations per individual at 0.51. Given these parameters, we determined that 300 individuals were needed in both the intervention and waitlist arms of this RCT. In order to allow for 20% attrition from baseline to follow-up, we increased the final recruitment goal to 720 individuals total (240 per site).

sampsi 9.5 9.1, sd1(1.6) sd2(1.9) method(ancova) pre(1) post(1) r1(.51) power(0.9)

Estimated sample size for two samples with repeated measures

Assumptions:

alpha =	0.0500	(two-sided)
power =	0.9000	
m1 =	9.5	
m2 =	9.1	
sd1 =	1.6	
sd2 =	1.9	
n2/n1 =	1.00	
number of follow-up measurements =	1	
number of baseline measurements =	1	
correlation between baseline & follow-up =	0.510	

Method: ANCOVA

relative efficiency =	1.352
adjustment to sd =	0.860
adjusted sd1 =	1.376
adjusted sd2 =	1.634

Estimated required sample sizes:

n1 =	300
n2 =	300

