13.5.2 Health care utilization indicators and hypotheses

One of the four arms of the intervention is the active referral to a primary care provider if the participant does not have one at the time of enrollment. In addition, the self-management support (SMS) activities in the intervention are designed to reinforce engagement of the participant with the primary care provider as a component of their diabetes management. Thus, our primary indicator will be change in the reported utilization of primary care services, as assessed by self-reported data and provider reports where available.

Our hypothesis is that the intervention participants will have increased engagement with their primary care provider when compared to the control group, and when compared to their level of engagement prior to the intervention. Because this particular model is unique in its use of food pantries as a point of outreach and support and its incorporation of a diabetes-focused food security intervention, there is no prior literature that directly informs our hypothesis development. However, we can draw some insight for hypothesis development from other studies of the impact of self-management support models on health care utilization. For example, Hamid et al. (2014) reported on a cluster-randomized design used to assign 268 diabetes patients to a nurse-community health worker intervention or usual care. Hospitalizations, emergency department, and primary care physician visits were collected retrospectively for one year prior to, and during, the intervention to assess changes in health care utilization. Adjusted incidence rate ratios for primary care physician visits were significantly higher in the community health worker intervention relative to the usual care. The authors found no main intervention effect on emergency department utilization, but visits in the prior year modified the intervention effect on emergency department visits. Increased primary care physician utilization was associated with greater decreases in HbA1c.

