Appendix AV – Barriers to Participation in FAITH-DM Activities Form

Barriers to Participation in FAITH-DM Activities

Instructions: Complete this form to document information participants provide about challenges / barriers to taking part in study activities. Return completed forms to the Research Assistant.

Date: _____

Participant ID#: _____

FAITH-DM Service Discussed by Participant: (Check any and all that apply)

- A1C / Blood Glucose Screening and Monitoring
- Food Packages
- Diabetes Education
- Primary Care Provider Referral or Appointments / Visits
- Other (please specify): _____

Type of Concern(s) or Barrier(s) that Participant Identified:

- Transportation (e.g., availability, cost)
- Time Conflicts (e.g., can't make the times when food distribution, education classes or clinic appointments are available)
- Food Package Concerns (e.g., doesn't like foods provided, volume is more than household can use)
- Costs of Primary Care Visits (e.g., can't afford copay, or paying out of pocket if no insurance)
- Hospitalization / illness / homebound:
- Other (please specify): _____

Additional Notes (use this space to provide details you think are helpful to understand the participant's concerns):

For Use by Research Assistant:

Date entered into ACCESS: _____

Date reported* to site manager and/or FA Project Manager ([name]): _____

**Report if issue(s) may require revision to study elements and/or processes.*

NOTE: *This form may contain protected health information – staff must keep this data secure. Once data is entered into Access database, securely store and/or destroy form according to study protocols.*

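### The engaged versus less-engaged comparison in Section 13.4.4 cannot show that the treatment effect is larger in engaged participants, and should be reported as descriptive only

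*Combined protocol and SAP*

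**What the plan says.** Hypothesis 1a in Section 13.4.3 is worded in terms of effect size: "we also hypothesize that the effect sizes will be largest among those who completed a minimum amount of exposure to all intervention components". Engagement has three parts, fixed in advance: collecting 80% of the food boxes, attending both classes, and "having at least 1 primary care visit over the 6-month follow-up period". All three are behaviours after randomization.

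The per-protocol/exposure paragraph of Section 13.4.4 takes participants with HbA1c at both baseline and follow-up and asks whether those who count as engaged "in the program (overall and by specific intervention component) had larger effects than those who were less engaged". It acknowledges that the benefit of randomization is gone and adds age, gender, race/ethnicity, education, language and site to the model. It writes out no model equation and does not say how the control arm enters.

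Section 3.4.1 restricts the classes to the intervention arm, and Section 3.6 keeps all intervention components from controls until T6. Section 13.5 collects primary care visits in both arms at T6, by self-report and by provider survey.

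**The concern.** The null hypothesis that matches 1a is that the intervention has the same effect in people who engage and people who do not. Testing it requires knowing how each kind of person would have fared without the intervention. Controls cannot be sorted by box collection or class attendance, so the planned comparison does not supply that. It compares two self-selected groups within one arm. If people who attend reliably would have had lower HbA1c anyway, the analysis can report larger effects when the effect is identical in everyone, or absent. If people in poorer health engage more, a real gain from fuller exposure can be hidden. At stake is a prespecified statement that full exposure works better.

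**Working it through.** **Inputs from Section 13.4.1.** Difference 0.4 (9.5 v 9.1), SDs 1.6 and 1.9, correlation 0.51, two-sided alpha 0.05, power 90%, one baseline and one follow-up measure.

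**The plan's own figure.** n per arm = (1.6² + 1.9²)(1 − 0.51²)(1.960 + 1.282)² / 0.4² = 6.17 × 0.7399 × 10.51 / 0.16 = 299.8, rounded up to 300. This agrees with the plan, where "we determined that 300 individuals were needed in both the intervention and waitlist arms". The documents give no power or error rate for the exposure analysis.

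**What the contrast estimates.** If each engagement group is set against all controls,

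(engaged − control) − (less engaged − control) = engaged − less engaged.

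In simulation without covariates, the two-arm contrast and the within-arm difference agreed to about 1e-14. With covariates, the controls contribute only through the pooled covariate slopes.

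**Rejection rate when the effect is the same in everyone.** Assumptions not in the documents: share engaged p from 20% to 50%, and a prognostic gap g in HbA1c points left after adjustment. Residual SD = 1.9 × √(1 − 0.51²) = 1.634, which credits the plan with keeping baseline HbA1c in the model. With 300 analysed in the intervention arm,

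SE = 1.634 × √(1/(300p) + 1/(300(1 − p)))

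rejection = Φ(g/SE − 1.96) + Φ(−g/SE − 1.96).

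For example, at p = 0.5 and g = 0.4, SE = 0.189, g/SE = 2.12, and rejection = 56%.

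| Share engaged | g = 0 | g = 0.2 | g = 0.3 | g = 0.4 |
|---|---|---|---|---|
| 20% | 5% | 13.6% | 24.6% | 39.6% |
| 30% | 5% | 16.3% | 30.8% | 49.3% |
| 40% | 5% | 18.0% | 34.4% | 54.7% |
| 50% | 5% | 18.5% | 35.6% | 56.3% |

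If 20% of the 720 recruited are lost, 288 per arm remain. The ranges become 13-18% at g = 0.2 and 38-55% at g = 0.4.

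**Does a real treatment effect matter?** In 4,000 simulated trials (40% engaged, gap 0.4, Huber-White errors, baseline HbA1c only), rejection was 55% with no treatment effect and 55% with a constant 0.4-point effect. The test does not separate prognosis from benefit.

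**What adjustment achieves.** Same setting, with a covariate related to engagement added: rejection is 46-47% if it carries none of the gap, 16% if it carries half, and 5.4% if it carries all.

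**The opposite direction.** Suppose engaged participants truly gain an extra 0.5 points and p = 0.5 (SE 0.189). The chance of a significant result in the expected direction is Φ(0.5/0.189 − 1.96), about 75%. If their prognosis is 0.2 worse it is Φ(0.3/0.189 − 1.96), about 35%. If it is 0.4 worse it is Φ(0.1/0.189 − 1.96), about 8%.

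**A contrast that keeps the controls.** A treatment-by-baseline-predictor interaction, with the predictor measured in both arms before randomization, rejected in 4.8-5.7% of trials in every scenario. It holds its level but has little power. For an extra 0.5-point effect and no gap, simulated power was about 5-23% for scores with AUC from about 0.61 to 0.86, even with the score treated as known.

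**The case against.** The plan does not hide the problem. It says that randomization is lost, keeps this analysis apart from the intent-to-treat estimate, and names adjustment variables. If those variables carried the whole prognostic difference, the 5% level would be restored. All of this stands. What the concession does not change is the conclusion that the text still permits, namely larger effects.

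A reader might infer that the test will often give a false positive. The documents do not support that. Neither the engaged share nor the residual gap is documented, and a gap of 0.4 would equal the whole effect that the trial is designed to detect. Appendix AV lists "Hospitalization / illness / homebound" among the barriers to taking part, but it is a blank form without frequencies. The finding cited in Section 13.5.2, "Increased primary care physician utilization was associated with greater decreases in HbA1c", comes from a trial whose intervention itself raised visits, so it does not isolate prognosis. These show that causes of engagement outside the adjustment list are plausible; they do not size the gap.

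A reader might also infer that the controls cancel for every component. Primary care visits are recorded in both arms, so they need not cancel there. An arm-by-visit model is not specified, however, and it would condition on a post-randomization variable that the intervention is meant to change.

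A third inference is that, for participants who already have a provider, the visit is merely usual care and should leave the definition. Section 3.2.1 alone could be read that way, but other sections point against it. Under Section 7.7.2.1 only intervention participants' providers receive the screening results. Section 3.4.2 has staff encourage contact with the provider. Section 13.5.2 says that self-management support is meant to strengthen that relationship.

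**Conclusion.** The concern holds with limits. On the overall definition, and for boxes and classes, the planned comparison estimates a difference in outcome between self-selected groups and cannot confirm hypothesis 1a. With no difference in effect it can reject in about 14-19% of trials at a residual gap of 0.2 points and about 40-56% at 0.4, given 20-50% engaged. With no residual gap it holds 5%. The mechanism follows from the design; the size rests on assumptions that the documents cannot settle. The primary care component is a partial exception. The analysis is secondary, and the primary ANCOVA is not touched.

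**What to change.** In Section 13.4.4, state that the engaged versus less-engaged comparison, overall and by component, is a descriptive, non-randomized association, and that it will not be reported as evidence of larger effects or as confirming hypothesis 1a. Leave the engagement definition in Section 13.4.3 as it is.

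Optionally, add an exploratory interaction between treatment and an engagement score predicted from baseline variables and assigned in both arms. It keeps the randomized controls, but the SAP should state its low power, so it is no replacement as a confirmatory test. If the score uses baseline HbA1c or food security, a positive result could reflect the modifiers named in hypothesis 1b.

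The cost is a few sentences and, if the option is taken, some analysis time; no new data, visits or participants are needed. The downside is that hypothesis 1a is left without a confirmatory test.
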